10.2 Modified capture-recapture methods

Capture-recapture (CRC) methods were originally developed in biology for estimating animal populations by sampling and marking the members of a population at a given time and then resampling the population at a subsequent time. The population size is then estimated by using the sample sizes and the number of members common to both samples. This methodology was later adapted and recommended to use for PSE of key populations by UNAIDS.

The CRC models have four assumptions. First, the population is closed. Second, the individuals in the first sample can be identified in the second sample. Third, the two samples are independent—the probability of being selected in one sample does not affect the probability of being selected in the other sample. Fourth, all individuals have equal probability of inclusion in each of the samples.

Separate CRC studies of national scale were not feasible in Ukraine, therefore modified approaches were used in conjunction with IBBS rounds since 2015.

One modification uses participation in IBBS as a first “capture”. Each subsequent round asks the participants about participation in the previous survey, providing a “recapture”. The 2023 IBBS round will also include the questions about prior participation in the IBBS in 2017 and 2020 to produce two population size estimates that will be included in aggregated analysis.

In another modification, unique objects are distributed in the population, and the number of people receiving the objects serves as a first “capture”. The type of unique object is determined according to the following criteria: acceptable and have intrinsic value (utility); useful to keep, but do not have commercial value that may facilitate the sale or trade for other things. The objects are distributed to individuals meeting the definition of the target population, in as many locations within the study area as possible. Starting one or two weeks after the distribution of the object, the survey asks whether the participants received the objects, serving as a “recapture”.

The total population size is calculated using the Lincoln–Peterson formula:

$$N = \frac{(S_1 * S_2)}{R}$$

where:

N – estimate of total population size

S_1 – number of persons captured by the first “capture”

S_2 – number of persons captured by the second “capture” (the survey sample size)

R – number of survey participants reporting captured in the first “capture”

Variance will be calculated by using the following formula:

$$Var(N) = \frac{(S_1 * S_2 * (S_1 - R) * (S_2 - R))}{R^3}$$

95% confidence interval will be calculated by using the following formula:

$$95\% CI: N \pm 1.96 * \sqrt{Var(N)}$$

For the 2023 PSE round will use two different unique objects to improve accuracy of the method. During the formative assessment, the Regional Working Group, will prepare a list – as exhaustive as possible – of the venues where PWID can be found. On a specified date, approximately two weeks prior to the start of IBBS data collection, designated representatives of the regional working groups will visit **all** venues and distribute the first unique object to the PWID present at the venue and who meet eligibility criteria (same as for IBBS, Annex 8). Results of distribution will be recorded in the Form (Annex 36. Unique Object Distribution Form). One week after that, a second visit to **all** venues will be done to distribute the second object, results will also be recorded in the Form. If it will not be feasible to visit all locations within the limited time frame, the venues for each visit will be selected randomly and independently (no overlap is required), to ensure that samples are independent. According to the guidelines¹⁵, the number of unique objects should be at least twice that of the target sample size. Since the sample size in each city will be equal to 500, the number of unique objects of each type to be distributed is 1000, total 2000 per city, or 4,000 in two cities. The cities will be selected by the National Working Group.

The following log-linear regression model will be used to estimate population size based on three 'captures'¹⁶.

$$\log E(Z_{ijk}) = u + u1I(i = 1) + u2I(j = 1) + u3I(k = 1) + u12I(i = j = 1)$$

The model estimates the log expected count of the population size for a 3-list capture-recapture analysis and adjusts for a positive (or negative) dependency between lists i and j. This model allows to relax the assumption of independency between captures by controlling for list dependencies through interaction terms.

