4.4 Sample size and power calculation

To calculate the sample size, a design effect was empirically estimated in the 2020 IBBS data set using the Gile's SS estimator based on the actual network size in "RDS" package in R v.4.0.5 (Table).

	HIV prevalence				Viral suppression			
	Est.	95% CI LL	95% CI UL	D.Eff.	Est.	95% CI LL	95% CI UL	D.Eff.
Bila Tserkva	16.1%	10.2%	21.9%	3.11	77.7%	66.6%	88.7%	2.39
Dnipro	26.5%	19.8%	33.2%	2.78	68.8%	54.8%	82.6%	3.56
Ivano-Frankivsk	9.3%	5.8%	12.9%	2.61	89.3%	82.8%	96.4%	1.44
Kirovohrad	10.2%	7.0%	13.4%	1.80	74.2%	61.4%	87.3%	2.70

Kryvyi Rih	21.9%	16.1%	27.7%	2.13	70.6%	59.9%	81.1%	1.72
Kyiv	18.2%	12.9%	23.5%	3.27	86.0%	77.0%	95.0%	2.96
Mariupil	30.5%	25.3%	35.6%	2.11	80.9%	72.7%	89.1%	2.21
Mykolaiv	33.2%	27.5%	38.9%	2.88	76.4%	68.3%	84.4%	2.49
Odessa	21.2%	15.3%	27.1%	2.50	80.7%	73.4%	87.9%	1.31
Kharkiv	7.5%	4.1%	11.0%	2.12	90.9%	91.0%	91.0%	-
Khmelnytskyi	29.7%	23.7%	35.7%	2.47	81.9%	74.3%	89.3%	1.91
Cherkasy	38.4%	31.4%	45.6%	2.43	86.5%	80.1%	93.0%	1.61

As shown, the design effect for HIV prevalence ranges from 1.8 to 3.3, and for viral suppression from 1.3 to 3.6. Therefore, a conservative value of 3.0 is used for the following sample size calculation.

The calculation was made for *the single sentinel cluster* sample, with expected HIV prevalence of 21% and 44% viral suppression (combined weighted estimate using 2020 round data for 5 cities and 2017 data for Lviv). Based on the simple asymptotic CI formula,¹¹ 0.05 probability of type I error, anticipated 5% of missing data, and 14% desired precision level for the viral suppression indicator (e.g. 44±7%), the resulting sample size should be 2914.

[figure not shown]
In order to simplify trend analysis across rounds, the total sample will be distributed evenly across participating cities, yielding a rounded target sample size of 500 in each city. This result corresponds to the standard universal sample size used in the US NHBS-IDU.¹² At the city level, assuming the design effect of 3.0 and 5% of missing data (e.g. incomplete data entry, entry errors), a sample size of 500 will provide ~16% precision for a maximally-conservative estimated prevalence for any indicator – 50% (i.e. 50±8%, the interval will be narrower for proportions closer to extremes, either 0 or 100%).

The same target sample size will be used for each additional city (outside the sentinel cluster).

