10.1 Multiplier method

The multiplier method is based on availability of at least two overlapping data sources specific to the population of interest, one being a count or registry of unique individuals belonging to the population, and another one being a representative survey that assessed whether the participants are present in the first data source. The data sources have to be independent of each other; define the target group in the same way; present the same time period, age and target group geography; be of sufficient data quality.

The formula to calculate the population size using the multiplier method is: $N = M/P$, Where:

N = Estimated Size

P = Proportion of survey participants who reported belonging to the registry (receiving the service, the object, or participating in the survey).

M = Number of individuals in the registry.

The 95% confidence intervals for proportions calculated for descriptive statistics using bootstrapping method with RDS weights will be used to calculate the lower- and upper limits for the population estimates.

The following data sources and indicators will be used for the multiplier method:

#	PSE indicator	Questionnaire item	Existing registry	Data provider
1	Registration in drug treatment clinics	Are you registered with the state narcological clinic in connection with drugs abuse or addiction?	Currently undetermined. Previously: Reporting form No.11 "Report on the morbidity of individuals with mental and behavioral disorders due to psychoactive substance use", annual. Table 2120 "Number of individuals with mental disorders due to intravenous drug use". Indicator: "among people under the supervision at the end of the reporting period".	Regional and city state drug treatment clinics.

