10.4.2 Estimates triangulation

Several estimates, calculated at a local level, will represent an estimation range for the number of PWID. This allows to compare the validity of individual methods and to define the most probable range at a city level. The final estimate of the group size is determined by intersection of the maximum number of separate assessment ranges and by averaging. A PSE method called anchored multiplier, that allows synthesizing several population size estimates into a single consensus estimate, is also planned. Anchored Multiplier calculator¹⁸, uses a Bayesian simulation model to combine empirical estimates. The calculator is suitable for entering data into beta distribution, which reflects data "strength". "Stronger" data (with narrower confidence interval) will have greater impact on the final estimate than "weaker" data (with wider confidence interval). The single city-level consensus estimates will be considered final and will be used for further calculations.

¹⁸ <https://globalhealthsciences.ucsf.edu/resources/tools>

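### Capture-recapture intervals in section 10.2 treat the RDS survey as a simple random sample; at the protocol's planning design effect of 3.0 they are 1.73 times too narrow (1.14 to 1.90 over its reported range)

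*Protocol*

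**What the plan says.** Section 10.2 uses the 2023 survey as the second capture. S2 is its sample size, R is the count of respondents who report the first capture, and N = S1×S2/R. It continues: "Variance will be calculated by using the following formula", namely Var(N) = S1×S2×(S1−R)×(S2−R)/R³, with limits N ± 1.96×√Var(N). Neither a weight nor a design effect appears, and equal inclusion probability is listed among the assumptions.

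Two kinds of first capture feed these formulas. One is unique objects, 1000 of each of two types per city, in two cities. The other is "participation in the IBBS in 2017 and 2020 to produce two population size estimates that will be included in aggregated analysis". The same section lists the assumptions of the method, beginning "First, the population is closed".

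Elsewhere the survey is treated as an RDS sample:

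- Section 4.4 reports that "the design effect for HIV prevalence ranges from 1.8 to 3.3, and for viral suppression from 1.3 to 3.6" in 2020. It adds: "Therefore, a conservative value of 3.0 is used for the following sample size calculation". It then applies 3.0 at city level to any indicator.
- Sections 9.1 and 9.2 apply RDS weights to all descriptive statistics, including their confidence intervals.
- Section 10.1 defines its survey proportion P to cover "receiving the service, the object, or participating in the survey". For the limits of the size estimate: "The 95% confidence intervals for proportions calculated for descriptive statistics using bootstrapping method with RDS weights will be used".

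Section 10.4.2 combines the estimates. In the anchored multiplier, stronger data ("with narrower confidence interval) will have greater impact on the final estimate than" weaker data) pull the result further, and the consensus is final for later calculations.

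**The concern.** R/S2 is a proportion estimated from the RDS survey, exactly as P is in section 10.1. RDS respondents are linked by recruitment chains and enter with unequal probability, so the proportion varies more than under simple random sampling. Section 4.4 quantifies that extra variation for two indicators. Section 10.2 leaves it out, so its intervals are too narrow.

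The understatement is carried forward because section 10.4.2 treats interval width as a measure of strength. Inputs from section 10.1 carry RDS bootstrap intervals and the two-sample inputs from section 10.2 do not, so the two sets are not compared on equal terms. City sizes then enter the additional weighting in section 9.2, the trend weights in section 9.4 and the count of PWID living with HIV in section 9.6.

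The prior-round recaptures raise a further problem. They span three to six years that include a war, section 4.3 describes significant migration in and out of some study cities, and eligibility requires injection in the last 30 days. Earlier participants who moved away or stopped injecting cannot be recaptured, so the closed-population assumption is in doubt.

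**Working it through.** **Inputs.** S1 = 1000 per object type and S2 = 500 per city (section 10.2); design effect 3.0, with a reported range of 1.3 to 3.6 (section 4.4). R = 50 is an illustration, corresponding to N = 10,000; Kharkiv's 2017 figure in the Annex is 9,900.

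**1. The protocol's own use of 3.0.** City precision at 50% with 5% missing: 1.96×√(3×0.25/475) = 0.078, a full width of 15.6% against the stated ~16%. Sentinel sample: 3×1.96²×0.44×0.56/0.07² = 579.5 HIV-positive; /0.21 = 2,760; /0.95 = 2,905 against the stated 2,914. Both agree closely, so 3.0 is the working design effect for this survey. The protocol states no numerical capture-recapture interval to reproduce.

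**2. What the variance formula is.** Put p = R/S2 and N = S1/p. With binomial variance p(1−p)/S2, the delta method gives Var(N) = S1²×S2×(S2−R)/R³. Multiplying by the finite-population factor (S1−R)/S1 gives S1×S2×(S1−R)×(S2−R)/R³, which is exactly the formula in section 10.2. Its design effect is 1.

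**3. The example.** Var(N) = 1000×500×950×450/50³ = 1,710,000; SE = 1,308; half-width 1.96×1,308 ≈ 2,563. With design effect 3.0, keeping the finite-population factor, the half-width is 2,563×√3 ≈ 4,440. The variance ratio is exactly 3.0 and the width ratio 1.73. Without the finite-population factor, as for S1/P in section 10.1, the half-width is about 4,555.

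**4. Coverage and range.** Coverage of the nominal 95% interval is 2Φ(1.96/√D) − 1 for design effect D.

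| D | Width ratio √D | Coverage |
|---|---|---|
| 1.3 | 1.14 | 91% |
| 1.8 | 1.34 | 86% |
| 2.5 | 1.58 | 79% |
| 3.0 | 1.73 | 74% |
| 3.6 | 1.90 | 70% |

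The 2.5 row is close to the median of the 2020 HIV-prevalence column in section 4.4. Beta-binomial simulation at D = 3 with S1 = 1000 and S2 = 500 gave coverage of 73%, 75% and 82% for N = 4,600, 9,900 and 20,100. Under simple random sampling the same interval covered 94% to 95%, so the formula works for the design it assumes.

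**5. Effect by city size at D = 3.** The Annex sizes show the scale only, because the two object cities are not named. Cherkasy (4,600): ±16% becomes ±27%. Kharkiv (9,900): ±25% becomes ±44%. Kyiv (33,700): ±50% becomes ±86%.

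**6. Prior-round recapture.** If a fraction a of earlier participants is no longer in the population, expected R falls by (1−a), and current N is overstated by 1/(1−a) − 1. The document gives no value for a; as an illustration, 20% gives 25% and 50% gives 100%. The 2020 recapture is possible in five of the ten cities: section 4.3 says the four additional cities were not in that round, and section 4.4 takes Lviv's data from 2017.

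**The case against.** Several objections have force.

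- **The factor 1.73 is not a fact about these data.** Section 4.4 calls 3.0 conservative, and its values are for HIV prevalence and viral suppression. The range must be shown. The direction does not change, since every reported design effect exceeds 1.
- **A reader might infer that capture-recapture gets three times too much weight in the consensus, or dominates it.** The document does not show this. Three-fold is the relative precision weight at D = 3. If true variances were equal, one capture-recapture estimate among eleven others would rise from 1/12 (8%) to 3/14 (21%), and four among eleven others from 4/15 (27%) to 12/23 (52%): 2.6 and 2.0 times. The calculator's exact weighting is not given, and section 10.4.2 also describes intersecting ranges and averaging. Multipliers with large P can be tighter anyway: at n = 500 and D = 3, P = 60% gives 1.96×√(3×0.4/(0.6×500)) = ±12%, against ±25.6% uncorrected in the example. At the same P of 10%, however, a section 10.1 interval would be ±45.5%.
- **A reader might infer that the protocol specifies two competing estimates of one quantity.** Only the general definition of P in section 10.1 mentions objects and prior surveys; its eleven listed indicators do not. What stands is that the same kind of proportion is handled in two ways.
- **Scope.** Objects are used in two cities only. Prior-round estimates use the same formulas more widely, but a small R already makes them imprecise: in Kyiv, assuming 500 earlier participants, R ≈ 500×500/33,700 ≈ 7 and the uncorrected interval is about ±71%.
- **Existing safeguards.** The plausibility range in section 10.4.1 removes extreme estimates but does not widen intervals. The three-list log-linear model relaxes independence between lists, which is a reason to keep it, but as written it uses raw cell counts and does not address the RDS design.
- **Reach.** In section 9.6 only the first cascade row uses population size, so a claim that the whole cascade is distorted would go too far.

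**Conclusion.** The point holds. Section 10.2 prescribes a simple-random-sampling variance for a proportion that the protocol otherwise treats as RDS data. At the planning design effect of 3.0 the variance is understated 3.0-fold, the interval is 1.73 times too narrow, and nominal 95% coverage is about 74%. Over 1.3 to 3.6 the interval is 1.14 to 1.90 times too narrow, with coverage of about 91% to 70%. These figures assume that the design effect for object receipt or prior participation lies within the range reported for other indicators.

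The estimates gain unearned relative precision weight in section 10.4.2, but the resulting shift in the consensus cannot be computed from the document. Unweighted counts may also bias the point estimate if network size is related to capture; neither sign nor size can be derived. The closed-population conflict is real for the 2017 and 2020 recaptures, but its size depends on an unknown loss fraction. The change should be made before the population size analysis.

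**What to change.** - In section 10.2, compute the two-sample object and prior-survey estimates as N = S1/P, with the RDS-weighted P and the RDS bootstrap interval of section 10.1. Replace the variance and interval formulas, and enter these versions in the consensus.
- Keep the three-list log-linear model, but fit it to RDS-weighted counts with a bootstrap interval. Otherwise report it outside the width-weighted consensus.
- Show the consensus with and without the 2017 and 2020 recaptures, and state the closed-population conflict beside them.

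The cost is revised wording, wider intervals and a re-run of code already planned for section 10.1. The weighted three-list fit and the second consensus run are modest extra programming. No new data are needed.

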16.0 Annex. Selection of cities for the 2023 PWID IBBS

Region	City	PWID population 2017	HIV prevalence 2020	Viral suppression 2020	Number of IBBS rounds participated 2007-2020	Selection for the 2023 round
AR Crimea	Simferopol				6	
Vinnytsia	Vinnytsia	5400			5	
Volyn	Lutsk	1800			6	
Dnipropetrovsk	Dnipro	20100	23.0%	33.0%	8	sentinel
Dnipropetrovsk	Kryvyi Rih	13300	23.7%	14.1%	4	
Donetsk	Donetsk	11700			6	
Donetsk	Mariupil		29.4%	38.8%	2	
Zhytomyr	Zhytomyr	2600			5	
Zakarpattia	Uzhgorod	1400			5	
Zaporizhzhia	Zaporizhzhia	7900			5	additional
Zaporizhzhia	Melitopol	3400			1	
Ivano-Frankivsk	Ivano-Frankivsk	2000	10.8%	61.5%	6	
Kyiv	Bila Tserkva	2700	15.9%	43.3%	5	
Kyiv	Vasylkiv	1300			3	
Kyiv	Fastiv	1200			3	
Kirovohrad	Kropyvnytskyi	5900	11.9%	28.4%	7	
Lugansk	Lugansk				5	
Lugansk	Sieverodonetsk	900			2	
Lviv	Lviv	6400			5	sentinel
Mykolaiv	Mykolaiv	8500	27.3%	56.4%	8	
Odesa	Odesa	21700	20.4%	42.1%	7	sentinel
Poltava	Poltava	4300			6	
Rivne	Rivne	3500			5	additional
Sumy	Sumy	7800			6	
Ternopil	Ternopil	3200			5	
Kharkiv	Kharkiv	9900	7.1%	20.0%	7	sentinel
Kherson	Kherson	4500			6	additional
Khmelnytskyi	Khmelnytskyi	5200	27.5%	53.2%	6	
Cherkasy	Cherkasy	4600	34.6%	62.1%	8	sentinel
Chernivtsi	Chernivtsi	3700			5	
Chernihiv	Chernihiv	4400			5	additional
Kyiv City	Kyiv City	33700	16.6%	39.6%	8	sentinel
Sevastopol	Sevastopol	6600			4

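### Section 10.2 uses the uncorrected Lincoln-Petersen ratio and a symmetric interval for the prior-IBBS capture-recapture estimates, where the three largest cities can expect only about 7 to 12 recaptures

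*Protocol*

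**What the plan says.** Section 10.2 fixes three formulas for two-sample capture-recapture:

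- Point estimate: "The total population size is calculated using the Lincoln–Peterson formula", that is N = S1*S2/R.
- Variance: "Variance will be calculated by using the following formula", that is S1*S2*(S1 − R)*(S2 − R)/R³.
- Interval: "95% confidence interval will be calculated by using the following formula", that is N ± 1.96*sqrt(Var(N)).

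There is no small-sample correction and no rule for small or zero R.

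Two kinds of first capture are described. One is an earlier survey round: the questionnaire will include "questions about prior participation in the IBBS in 2017 and 2020 to produce two population size estimates", both of which enter the aggregated analysis. The other is unique objects in two cities still to be chosen: "the number of unique objects of each type to be distributed is 1000". A three-list log-linear model is also specified there.

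The second capture is the 2023 survey: "Since the sample size in each city will be equal to 500". The Annex on selection of cities (section 16.0) gives 2017 sizes of 33,700 for Kyiv, 21,700 for Odesa and 20,100 for Dnipro.

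**The concern.** The algebra is the standard large-sample form and is correct as such. But 1/R is convex, so the mean of S1*S2/R exceeds N when R is small, and the ratio has no value at R = 0. Its sampling distribution is skewed to the right, which an interval symmetric around N cannot follow.

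With 500 people in the 2023 survey and populations above 20,000, R is small when the first capture is an earlier round of ordinary size. The three cities affected hold 33,700 + 21,700 + 20,100 = 75,500 of the 96,400 PWID in the six sentinel cities (78%).

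Both the estimates and their intervals are used later. Section 10.4.2 works from the intersection of ranges, from averaging, and from an anchored multiplier that gives narrower intervals more weight. City sizes then serve as weights in sections 9.2 and 9.4.

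**Working it through.** **The plan's own figure.** The only sizing given for capture-recapture is the number of objects: 2 × 500 = 1,000 per type, × 2 types = 2,000 per city, × 2 cities = 4,000. This reproduces. The protocol gives no expected recaptures, bias or coverage.

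**Inputs.** S2 = 500 (section 10.2). N is the 2017 size in the Annex. S1 for the earlier rounds is not stated, so I use two values:

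- S1 = 500, an assumption.
- The 2020 size implied by the table in section 4.4, n = DEFF*p(1 − p)/SE², with SE = interval width/3.92.
  - Kyiv: SE = (0.235 − 0.129)/3.92 = 0.0270; n = 3.27 × 0.182 × 0.818/0.0270² ≈ 666.
  - Odesa: n = 2.50 × 0.212 × 0.788/0.0301² ≈ 461.
  - Dnipro: n = 2.78 × 0.265 × 0.735/0.0342² ≈ 463.

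The 2017 sizes cannot be derived.

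**Method.** Under simple random sampling from a closed population, R is hypergeometric with mean S1*S2/N. I summed over its exact distribution, given R > 0.

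| City | S1 | Expected R | Mean bias of S1*S2/R | Median bias | Coverage of stated interval |
|---|---|---|---|---|---|
| Kyiv | 500 | 7.4 | +18.6% | +6.0% | 92.8% |
| Odesa | 500 | 11.5 | +10.3% | +4.7% | 92.7% |
| Dnipro | 500 | 12.4 | +9.3% | +3.6% | 92.4% |
| Kyiv | 666 | 9.9 | +12.7% | −1.2% | 92.6% |
| Odesa | 461 | 10.6 | +11.4% | +6.2% | 93.1% |
| Dnipro | 463 | 11.5 | +10.2% | +4.7% | 92.8% |

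In Kyiv the mean bias is +30% at S1 = 300 and +12% at S1 = 700. With 1,000 objects it would be +7.5% in Kyiv, +4.4% in Odesa and +4.1% in Dnipro. In the seven smaller cities at S1 = 500, expected R is 25 to 71 and the bias is 1 to 4%.

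**Shape of the interval.** At S1 = S2 = 500 the lower limit is (250,000/R) × [1 − 1.96 × (500 − R)/(500 × sqrt(R))]. Over all R it peaks near 9,960, at R = 9. It therefore can never exceed the true size in these three cities, and every miss (7.2 to 7.6%) has its upper limit below N. At R = 3 the estimate is 83,333, the standard error 47,824 and the lower limit −10,401. In Kyiv about 6% of draws give a negative lower limit at S1 = 500, and 1% at S1 = 666.

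**Chapman's point estimate**, (S1 + 1)(S2 + 1)/(R + 1) − 1, at S1 = 500: mean bias is under 0.5% in all three cities. Relative root mean squared error falls from 0.70 to 0.40 in Kyiv, 0.43 to 0.32 in Odesa and 0.39 to 0.30 in Dnipro.

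**Intervals compared**, three cities, S1 = 500:

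| Interval | Coverage |
|---|---|
| Stated: N ± 1.96 SE | 92–93% |
| Chapman's variance, symmetric | 87–88% |
| Chapman's estimate and variance, log scale | 92–94% |
| Protocol's estimate and variance, log scale | 93–96% |

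The last one uses M = S1 + S2 − R, f = S1*S2/R − M and C = exp{1.96*sqrt(ln(1 + Var/f²))}, giving M + f/C to M + f*C. Its misses with the upper limit below N fall to 2.6 to 4.3%, about half, and no limit can be negative. Example at R = 7: estimate 35,714, SE 13,310, f = 34,721, C = 2.066. The interval is 17,797 to 72,735, against 9,627 to 61,801 as stated.

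**The case against.** Much of the case against a strong claim stands.

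- **The top of the range depends on an assumption.** The 19% needs S1 = 500 in Kyiv. The only 2020 size that can be inferred for Kyiv is nearer 666, which gives 13%.
- **The mean overstates the typical error.** It is driven by the right tail of 1/R. The median error is 4 to 6% at S1 = 500. Chapman's own median in Kyiv is −7%, so its gain lies in mean bias and mean squared error, not in the median. R = 0 has probability of about 0.0005 in Kyiv at S1 = 500.
- **Sampling error is larger.** The relative standard error is 28 to 36%, and the loss of coverage is only 2 to 3 points.
- **Later steps may dampen the bias.** Section 10.4.1 drops estimates outside a plausible range, the anchored multiplier gives wide intervals less weight, and many multiplier estimates and the successive-sampling method also enter.

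A reader might infer that all capture-recapture estimates, or the published city sizes, will be 9 to 19% too high. The documents do not support that. Unique objects give 4 to 8% in these cities and have a log-linear model as well, and smaller cities show 1 to 4%. The effect after aggregation is not demonstrated in size or direction. The calculation also assumes a closed population and independent simple random samples. The first capture is three to six years old, section 4.3 describes wartime migration, and sampling is by RDS. Out-migration lowers R and dependence between captures may raise it, so the sign of the total error is unknown.

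These points limit the size of the concern. They do not defend the formulas: the bias and the impossible lower limits are avoidable at almost no cost.

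**Conclusion.** The point holds for the two estimates that use 2017 and 2020 IBBS participation as first capture in Kyiv, Odesa and Dnipro. With S2 = 500, the 2017 Annex sizes and simple random sampling, the uncorrected ratio is too high on average by 9 to 19% at an assumed S1 of 500, and by 10 to 13% at the 2020 sizes implied by section 4.4. The symmetric interval falls slightly short of 95%, misses on one side only, and can give negative limits in Kyiv. This is a worthwhile refinement, not an error that undermines the survey.

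**What to change.** In section 10.2:

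1. Replace the point formula with Chapman's N = (S1 + 1)(S2 + 1)/(R + 1) − 1, which is also defined at R = 0.
2. Replace N ± 1.96 SE with the log-scale interval on the uncaptured number shown above, computed from the protocol's own S1*S2/R and its variance, or with an exact hypergeometric interval. Do not use Chapman's variance for the interval, since it brings no consistent gain on the log scale and is worse if symmetric. The log-scale form is undefined at R = 0, so name the exact interval for that case.
3. State the 2017 and 2020 sample size in each city that will serve as S1, so that expected recaptures can be read off in advance.

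This needs new formulas and one line of inputs. There is no extra data collection or field cost, and where R is large the results hardly change. It does not address RDS clustering, migration or dependence between captures, for which the section 10.2 variance has no term.

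### The three-capture log-linear model frees only one of three list pairs and equals a two-list Lincoln–Petersen estimate, so it does not relax independence between captures in general

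*Protocol*

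**What the plan says.** Protocol section 10.2 lists independence of the samples among its capture-recapture assumptions, and adds: "Fourth, all individuals have equal probability of inclusion in each of the samples".

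It then describes a three-capture design. "For the 2023 PSE round will use two different unique objects to improve accuracy of the method"; these are handed out at venues one week apart, and "the survey asks whether the participants received the objects, serving as a “recapture". For the analysis, "The following log-linear regression model will be used to estimate population size based on three 'captures". The formula has an intercept, three main effects and one interaction; it ends in "u3I(k = 1) + u12I(i = j = 1" and a closing bracket. There is no u13 or u23, no alternative model and no selection rule. The text does not say which capture is i, j or k.

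Two sentences describe what the model does. The first is limited: it "adjusts for a positive (or negative) dependency between lists i and j". The second is general and speaks of terms in the plural: "This model allows to relax the assumption of independency between captures by controlling for list dependencies through interaction terms".

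**The concern.** Three lists have three pairwise dependencies, and the printed model estimates one of them. A reader of the general sentence would conclude that dependence between object receipt and survey participation has been handled. In the natural order of the captures it has not.

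Such dependence is plausible. Objects go to people found at venues, and survey entry runs through peer networks (section 4.1), so visible and well-connected people may be likelier to be in both. The protocol itself relies on unequal inclusion in section 10.3, where larger networks are assumed to be recruited earlier.

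At stake are the city size estimate and its interval. Section 10.4.2 gives estimates with narrower intervals more influence on the consensus, so a biased estimate with a narrow interval gains weight. City sizes are later used for weighting (sections 9.2 and 9.4), and population size enters the count of PWID living with HIV (section 9.6).

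**Working it through.** **1. The plan's own figures.** Survey size per city is 500. Objects per type: 2 × 500 = 1,000; per city: 2 × 1,000 = 2,000; two cities: 2 × 2,000 = 4,000. These match section 10.2. The protocol states no population size or bias for the model.

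**2. Closed form of the printed model.** Let Zijk be the cell counts, with 1 meaning on the list and Z000 unseen. The model has 5 parameters for 7 observed cells. Because u12 saturates the i–j margin, the ratio Zij1/Zij0 is the same, exp(u3), for every (i, j). Its estimate is (Z101 + Z011 + Z111)/(Z100 + Z010 + Z110), and Z001 is fitted exactly. Hence

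Z000 = Z001 × (Z100 + Z010 + Z110)/(Z101 + Z011 + Z111).

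Now let A be the number on list i or list j, B the number on list k, and m the number in both A and B. Lincoln–Petersen leaves (A − m)(B − m)/m unseen, which is the same expression. So N = A × B/m. Poisson fits on 300 random tables for each possible interaction pair agree with this to a relative difference of 9e-15. Given A, the overlap between lists i and j does not affect the estimate.

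**3. Labelling.**

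| List k | Forced to independence |
|---|---|
| Survey (natural order) | survey–object 1 and survey–object 2 |
| Object 2 | object 2–survey and object 2–object 1 |
| Object 1 | object 1–survey and object 1–object 2 |

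Every row contains at least one object–survey pair.

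**4. Bias in expected counts, natural order.** Inputs: 1,000 of each object and survey 500 (section 10.2); true N 4,600 (Cherkasy) and 33,700 (Kyiv City), the smallest and largest 2017 figures among the sentinel cities in the annex. Assumed, not in the documents: object–object odds ratio 3, object–survey odds ratio 0.5 to 3, and no three-way interaction.

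| Object–survey odds ratio | True N 4,600 | True N 33,700 |
|---|---|---|
| 0.5 | 7,922 (+72%) | 66,334 (+97%) |
| 1 | 4,600 (0%) | 33,700 (0%) |
| 1.5 | 3,510 (−24%) | 22,837 (−32%) |
| 2 | 2,969 (−35%) | 17,415 (−48%) |
| 3 | 2,430 (−47%) | 12,009 (−64%) |

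For example, at odds ratio 2 and N = 4,600, A ≈ 1,607.5 and m ≈ 270.7, so A × B/m = 1,607.5 × 500/270.7 ≈ 2,969.

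**5. Shared visibility.** Simulation with gamma-distributed visibility (an assumption), 1,000 of each object, survey 500, N = 10,000. Entries are mean estimate over truth.

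| Correlation of venue and survey visibility | CV 0.5 | CV 0.8 |
|---|---|---|
| 1 (fully shared) | 0.83 | 0.66 |
| 0.5 | 0.91 | 0.80 |
| 0.25 | 0.96 | 0.89 |

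At CV 0.5 the nominal 95% interval missed the truth in about 72–75% of runs with full sharing, 28% at correlation 0.5 and 14% at 0.25. At CV 0 it missed in about 5–6%.

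**6. All three pairwise terms.** This model has 7 parameters for 7 cells. With no three-way interaction it recovers the true N in expected counts. Simulated 2.5–97.5% ranges with object–object odds ratio 3 and object–survey odds ratio 2:

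| True N | Printed model | All pairwise |
|---|---|---|
| 4,600 | 2,755–3,208 | 3,675–6,073 |
| 33,700 | 13,900–22,700 | 7,900–90,400 |

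The printed model's range excludes the truth in both rows. Under fully shared visibility the all-pairwise model is not unbiased either: its median ratio is 0.87–0.98 at CV 0.5–0.8 (N = 5,000–10,000). At CV 0.5 its range of estimate over truth is about 0.5–1.8 at N = 10,000; at N = 20,000 repeated runs put the lower limit at 0.12–0.27 and the upper at 2.8–3.1.

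**The case against.** The sentence before the general claim names lists i and j, so a careful reader can see which pair is freed. That stands: the claim is overstated, not wholly false. It still describes a property that the printed formula lacks.

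The second object is not wasted. The stated aim is better accuracy, and a larger first capture does improve precision.

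Several stronger readings are tempting, and the documents do not support them:

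- **That object–survey is the pair most likely to be dependent.** Both objects go to the same venue list a week apart, so object–object dependence may well be the strongest, and in the natural order u12 frees exactly that pair. The safeguard "the venues for each visit will be selected randomly and independently (no overlap is required), to ensure that samples are independent" applies only if not all venues can be visited. What can be said is that no comparable safeguard exists for object versus survey.
- **That the model certainly treats the survey as independent of both objects.** This depends on the labelling, which the protocol does not give.
- **That the interval will almost always miss.** That result needs fully shared visibility; at lower correlation the bias is smaller. Negative dependence reverses its sign.
- **That city sizes generally, or the count of PWID living with HIV, are wrong for this reason.** Objects are distributed in two of ten cities. There the result joins the multiplier estimates, the recaptures from earlier survey rounds and successive sampling, followed by a range check and triangulation. The check in section 10.4.1 removes only values outside its limits, so a moderate bias could pass.
- **That the all-pairwise model should become the main estimate.** It is saturated, so its fit cannot be checked; it assumes no three-way interaction; and it is close to uninformative in large cities.

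**Conclusion.** The point holds as a misdescribed and incomplete analysis. The algebra is exact and needs no assumption: one of three pairs is freed, and the estimate equals Lincoln–Petersen of list i or j against list k. Whether and how far city size is biased depends on an object–survey dependence that the documents do not quantify. Over the assumed range at N = 10,000 (visibility CV 0.5–0.8), the mean estimate is about 66–83% of the truth with fully shared visibility and 80–91% at correlation 0.5. With negative dependence it is too high.

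The printed model's interval reflects none of this uncertainty, and the triangulation rule rewards narrow intervals. The reach is limited to the two object cities and to one of several inputs there. The correction should be made, but the printed model need not be discarded.

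**What to change.** In section 10.2:

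1. State which captures are i, j and k.
2. Replace the general sentence: the printed model relaxes only the i–j dependence and assumes list k independent of both other lists.
3. Report beside it, as prespecified sensitivity analyses, models that add the object–survey terms (u13, u23, up to all three pairs). Carry the spread between models into the uncertainty used in section 10.4.2, instead of the printed model's interval alone.
4. Ensure that the number of people who received both objects is recorded at the second distribution. The three-list table needs it, and so does the printed model, because A is 1,000 + 1,000 minus that number if all objects are handed out. The distribution form is not shown and may already collect it.

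The cost is a few sentences, possibly one field on the form, and a few extra fits in two cities. The downside is wider intervals. Where N is about 20,000 or more (the 2017 figures for Kyiv, Odesa and Dnipro are 33,700, 21,700 and 20,100), the all-pairwise model will be very imprecise, so it belongs beside the printed model and should not replace it as the main estimate.
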